***Delineation of Sensorimotor Subtypes Underlying Residual Speech Errors
(C-RESULTS-SCED)***

Protocol NCT03736213

Document generated 2/2/2018

Narrative Study Protocol

Overview. At the group level, children with RSE show poorer auditory-perceptual and oral somatosensory sensitivity than typical individuals, but individuals differ in the extent to which each sensory domain is impacted. Based on their grounding in sensorimotor models of speech production, biofeedback treatment approaches can be predicted to be more or less successful for a given individual based on whether the enhanced feedback matches that individual's major area of sensory impairment. The objective of this aim is to evaluate how distinct deficit profiles mediate relative response to different types of biofeedback intervention using a single-case randomization design. The same randomization design will be replicated across 8 individuals hand-selected to feature a high degree of asymmetry in auditory versus somatosensory domains of perception. Our hypothesis is that visual-acoustic biofeedback will produce larger gains in individuals whose deficit primarily affects the specification of the auditory target, while ultrasound biofeedback will produce larger gains in individuals whose deficit primarily affects the oral somatosensory target.

All 8 participants will receive an equal dose of both types of biofeedback treatment (10 hours of ultrasound biofeedback and 10 hours of acoustic biofeedback) but with the order randomized in each day. Participants in Study 3 will receive a total of 20 hours (10 days) of treatment over a 5-week period. Our prior single-case studies for both types of biofeedback suggest that this dosage is sufficient to observe within-session Acquisition of correct /r/.

Randomization. In this single-case randomization design, each participant will receive an equal number of sessions of visual-acoustic and ultrasound biofeedback, with randomized allocation of treatment types to individual sessions. Randomization will be blocked, with each of day of treatment serving as a block; within each day/block, one hour of treatment will be randomly assigned to feature visual-acoustic and one to feature ultrasound treatment. Based on each participant's sensory profile, we will define a congruent condition and an incongruent condition--that is, the biofeedback type that is expected to be more effective and the type that is expected to be less effective. We define visual-acoustic biofeedback as the congruent condition and ultrasound biofeedback as the incongruent condition for individuals with a primary auditory deficit; the reverse is true in the case of a primary somatosensory deficit.

Intervention Delivery. The text below describes elements of treatment that are shared across traditional and biofeedback conditions (both ultrasound and visual-acoustic). All sessions will feature the same dosage of treatment and will follow the same structure. Treatment conditions will differ only in the nature of cues and feedback provided. Differences across treatment conditions are described below under Interventions.

Participants will receive treatment structured similarly to the procedures described for Phase 1 (Acquisition) in the C-RESULTS RCT, which focuses on eliciting /r/ at the syllable level. However, participants in Aim 3 (who will be required to fall in the “low response” group from Phase 0 of treatment) will receive a longer duration of Acquisition training (20 hrs/10 days over a 5 week period). The first 30 minutes of each session will consist of relatively unstructured, highly interactive pre-practice, designed to provide instruction on the phonetic requirements for /r/ and shaping strategies to transform the child's current productions into accurate /r/. The next 30 minutes will elicit up to 200 syllables or 30 minutes of practice, whichever occurs first. (This high level of intensity has been successfully achieved by members of our research team in previous and in ongoing studies.) Practice will occur in blocks of 10 consecutive trials on the same syllable (e.g., 10 /ra/), after which a new syllable will

be addressed (e.g., 10 /re/). After every fifth trial, the clinician will provide qualitative (knowledge of performance) feedback appropriate for the current treatment condition (acoustic or ultrasound). In addition, one randomly chosen token in each block of 10 trials will be flagged for acoustic measurement and will be elicited in a no-feedback condition. Thus, biofeedback will be made available in 90% of trials. To limit variability of practice, only 5 different syllables will be treated for each participant in the first two sessions of treatment, and we will add one new syllable in each subsequent block (of two sessions). Syllables that are targeted in treatment will be based on those that are the least accurate during Phase 0 (and if all syllables are at 0% accuracy then a common set of 5 syllables will be chosen). Participants will not complete Phase 2 (Generalization) as part of the design of Study 3, but for ethical reasons, they will be offered the opportunity to receive Generalization Training after completion of the Aim 3 protocol. This training would fall outside of the context of the study and will not be analyzed for research purposes.

***Protocol NCT03736213***

***Document generated 2/2/2018***

### **Statistical Design and Power: Study 3**

For inferential statistical analysis, a randomization test will be conducted for each participant. Each randomization test will compare the two biofeedback types (ultrasound and visual-acoustic) with respect to F3-F2 difference for the 25 /r/ trials measured in each session. In a previous randomization study comparing biofeedback and non-biofeedback treatment in 7 children with RSE, the median effect size of the difference between treatment conditions ( $d_2$ ) was calculated to be 3.0. Calculations using GPower indicate that our proposed within-participant comparison (10 observations in each condition) has 90% power to detect an effect of this magnitude. We do not currently have data to estimate the likely magnitude of the difference between visual-acoustic and ultrasound biofeedback conditions in individuals with asymmetric sensory profiles. However, relying on a precedent established in previous single-case studies of treatment efficacy and upheld throughout our own previous research, we will treat  $d_2 = 1.0$  as the minimum difference between conditions that will be considered clinically significant. (That is, the difference between conditions must be at least as great as the pooled standard deviation). Our proposed within-participant comparison has power of .80 to detect this minimum effect size of interest. In addition, these power calculations ignore the fact that we will have 20 observations in each session; models that incorporate the nested structure of the data would presumably reflect higher power.

Randomization tests are computed within-subject, and we propose to replicate this comparison across 8 participants. As described in **Aim 3**, participants enrolled in Study 3 will be required to exhibit an asymmetric profile of sensory sensitivity. This requirement for asymmetric sensory acuity will allow us to use within-subject comparisons to test the hypothesis that sensory acuity in a domain mediates response to the type of biofeedback that targets that domain. Although we do not yet have estimates of the prevalence of such asymmetries in the population of children with RSE, our pilot data suggest that asymmetric sensory profiles occur in roughly 8% of typically developing young adults. Assuming that asymmetries occur at the same rate in the population of children with RSE, our overall sample of 118 children is estimated to yield between 9 and 10 individuals who meet criteria for Study 3. Based on our previous work, we anticipate that not all participants will show a significant randomization test result, but those who do will show an advantage for the congruent over the incongruent condition, and not the reverse.

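### The two stated power figures cannot come from one calculation: .80 power at d2 = 1.0 implies more than .9999 at d2 = 3.0, not 90%, and the inputs behind the .80 are not given

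*SAP*

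**What the plan says.** The SAP, in Statistical Design and Power: Study 3, plans a separate randomization test for each child, comparing ultrasound with visual-acoustic biofeedback. It gives two power figures for that test.

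- At d2 = 3.0, the median from an earlier study of biofeedback against non-biofeedback treatment, GPower is said to show that "our proposed within-participant comparison (10 observations in each condition) has 90% power to detect an effect of this magnitude".
- At d2 = 1.0, the smallest difference to be treated as clinically significant: "Our proposed within-participant comparison has power of .80 to detect this minimum effect size of interest".

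The SAP explains d2 = 1.0 by saying that "the difference between conditions must be at least as great as the pooled standard deviation". It adds that "these power calculations ignore the fact that we will have 20 observations in each session", although earlier in the same section the outcome is the "F3-F2 difference for the 25 /r/ trials measured in each session".

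The Protocol, under Randomization, pairs the two conditions by day: "Randomization will be blocked, with each of day of treatment serving as a block". Each of the 10 treatment days has one session of each type.

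On expected results, the SAP says "we anticipate that not all participants will show a significant randomization test result" and that "those who do will show an advantage for the congruent over the incongruent condition, and not the reverse".

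Neither document states the alpha, the sidedness, the test chosen in GPower, the same-day correlation, or whether the pooled SD is of session values or of single trials.

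**The concern.** Both figures are attached to one comparison with one number of observations. On any one scale an effect of 3.0 is three times an effect of 1.0, so a test that already has .80 power at the smaller effect should be almost certain to detect the larger. A rise of only ten percentage points suggests that the two figures came from different calculations.

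That directs attention to the .80, the only power figure for the smallest effect of interest. The SAP says it has no data on the likely difference between the two biofeedback types, so d2 = 1.0 is the planning value. These are the only power figures given for the per-child tests. The SAP expects some children not to reach significance, and a reader who wants to judge how many should needs to know what the .80 rests on.

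**Working it through.** **Inputs from the documents.** 10 sessions per condition, paired within 10 days; d2 = 3.0 with stated power .90; d2 = 1.0 with stated power .80; d2 scaled by the pooled SD.

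**Assumptions.** Normal values, equal SDs, alpha .05 unless varied, and the same standardiser for both d2 values. Same-day correlation (rho) is not given; 0 to .7 is shown.

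**Formulas.** Noncentral-t power.

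- Unpaired: df = 18, noncentrality = d × √(10/2) = d × √5.
- Day-paired: df = 9, noncentrality = dz × √10, where dz = d / √(2(1 − rho)) if d is in units of a session-level pooled SD. At rho = .5, dz = d; at rho = 0, dz = d/1.414.

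**Step 1: reproduce the .80.** Take a paired test, two-sided .05, with 1.0 read as dz. Noncentrality is 1.0 × √10 = 3.16 on 9 df, and power is **.803**. The printed .80 is recovered, but on the SD of the within-day differences, not the pooled SD in the text.

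**Step 2: try to reproduce the 90% at d = 3.0.** At two-sided .05:

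- day-paired, rho = 0: noncentrality = (3.0/1.414) × √10 = 6.71; probability of missing the effect 4.2e-5, power .99996;
- day-paired, rho = .5: noncentrality = 9.49; probability of missing it 1.5e-10;
- unpaired: noncentrality = 3.0 × √5 = 6.71; probability of missing it 6.5e-6, power .99999.

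One-sided at rho = 0, the probability of missing it is 3.7e-6. None of these gives 90%.

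**Step 3: can the unstated alpha reconcile the pair?** Solve for the two-sided alpha that gives exactly .80 at d = 1.0. It is .198 / .104 / .049 / .028 / .012 at rho 0 / .3 / .5 / .6 / .7, and .181 unpaired. At each of these the probability of missing d = 3.0 is at most 2.0e-7, and the one-sided result is the same. In reverse, day-paired 90% at d = 3.0 needs a two-sided alpha between 8.7e-4 (rho 0) and 6.1e-6 (rho .7), which leaves power of only .045 down to .01 at d = 1.0. No alpha yields both figures.

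**Step 4: what effect does have 90% power?** With a session-level SD at alpha .05:

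| Test | rho 0 | .3 | .5 | .6 | .7 |
|---|---|---|---|---|---|
| Day-paired, two-sided | 1.63 | 1.37 | 1.15 | 1.03 | 0.89 |
| Day-paired, one-sided | 1.42 | 1.19 | 1.00 | 0.90 | 0.78 |

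Unpaired: 1.53 two-sided, 1.36 one-sided. All are far below 3.0.

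**Step 5: how far does the .80 depend on what is unstated?** Power at d2 = 1.0 with a session-level pooled SD, alpha .05:

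| Test | rho 0 | .3 | .5 | .6 | .7 |
|---|---|---|---|---|---|
| Day-paired, two-sided | .51 | .66 | .80 | .88 | .95 |
| Day-paired, one-sided | .66 | .79 | .90 | .95 | .98 |

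Unpaired: .56 two-sided, .69 one-sided. Paired power reaches .80 at rho = .496 two-sided or .313 one-sided.

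A simulation of the planned test itself (all 2^10 = 1,024 within-day assignments, 20,000 runs) agrees. At d = 1.0 it gives .502 / .658 / .797 / .876 / .950 two-sided and .657 / .795 / .897 / .944 / .983 one-sided; at d = 3.0, two-sided, .9999 at rho 0 and 1.00 from rho .3 upward.

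**Step 6: if the pooled SD is of single trials.** In units of the trial variance, a session mean of m trials has variance icc + (1 − icc)/m, where icc is the within-session correlation (not given). With m = 20, rho = 0, two-sided, power at d2 = 1.0 is .93 / .86 / .78 / .65 at icc .3 / .4 / .5 / .7. It is at least .80 when icc is at most about .48 (two-sided) or .67 (one-sided). With m = 25 these limits barely move (.483 and .674).

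**Step 7: number of significant children, if every true d2 were 1.0.** The printed figure implies 8 × .803 = 6.4 of 8. With a session-level SD and rho from 0 to .7, the range is 8 × .514 = 4.1 to 8 × .951 = 7.6 (two-sided), or 8 × .662 = 5.3 to 8 × .982 = 7.9 (one-sided).

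**The case against.** The strongest reply is that the proven error changes nothing. True power at 3.0 is higher than stated, the 3.0 comes from a different contrast, and the SAP itself moves on to d2 = 1.0. The .80 does reproduce, with common defaults: paired test, two-sided .05, 10 pairs. On that view this is a small correction plus a request for fuller reporting. That stands as far as the 90% goes. It does not dispose of the .80, because the calculation that returns .80 uses a different standardiser from the one the SAP describes. The two agree only if the same-day correlation is about .5, and no passage says so.

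Two further objections limit the alternatives. An expected direction of results is not a choice of a one-sided test. And the SAP's remark that the calculations ignore the repeated trials points to sessions as the unit, which makes a trial-level SD the less natural reading. Both are fair, and both alternatives remain conditional here; the text does not exclude either.

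It is also true that 0 to .7 is an assumed range and not a bound, that the counts of significant children assume every true d2 is 1.0 (which the SAP presents as a minimum, not an expected value), and that the SAP rests its expectation of some non-significant children on previous work and not on the .80. Alpha and sidedness may be set in the parent project's documents; the claim is only that they are absent from these two.

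**Conclusion.** The concern holds. The stated 90% at d2 = 3.0 is wrong given .80 at d2 = 1.0: for t-tests with 10 observations per condition and one standardiser for both effects, power at 3.0 exceeds .9999 whatever alpha is chosen to give the .80. The error runs in the safe direction and does not show the design to be underpowered.

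The .80 is not shown to be wrong, but it does not follow from the SAP's description of d2 without a further input. If the pooled SD is of session values, .80 needs a same-day correlation of about .50 (two-sided .05) or .31 (one-sided .05). A child with exactly the minimum effect of interest could have power anywhere from .51 to .95 two-sided over the assumed correlations. If the SD is of trials, the condition falls on the within-session correlation instead. All of this assumes normal values and equal SDs; simulation of the within-day randomization test gives closely matching power.

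**What to change.** 1. Delete the 90% at d2 = 3.0, or restate it as above 99%.
2. For the .80, state the alpha, the sidedness, the test (a randomization test with labels permuted within day, 1,024 assignments), the standardiser (pooled SD or SD of differences; session means or trials) and the assumed same-day correlation. Recompute power on those inputs.
3. If the inputs are two-sided .05 with a session-level pooled SD, report .80 as conditional on a same-day correlation of about .5, and show .51 (correlation 0) to .95 (correlation .7) as an illustrative range. If one-sided .05, the condition is about .31 and the range .66 to .98.
4. If the SD is of trials, also state the assumed within-session correlation and use one trial count; the section now gives both 25 and 20.

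The cost is SAP wording and one recomputation. Design, test and sample size stay as they are. The drawback for the sponsor is that the .80 becomes a conditional figure and may turn out less favourable.

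### The profile-by-type hypothesis gets only one test per child; the available text gives no between-profile test, no decision rule across children and no number per profile

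*SAP*

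**What the plan says.** The protocol's Overview states a two-part hypothesis. Its first part is that "visual-acoustic biofeedback will produce larger gains in individuals whose deficit primarily affects the specification of the auditory target". Its second part concerns children with the opposite profile and predicts that "ultrasound biofeedback will produce larger gains in individuals whose deficit primarily affects the oral somatosensory target". Together the parts make a profile-by-type interaction in which the better type changes with the profile. The sample is "8 individuals hand-selected to feature a high degree of asymmetry in auditory versus somatosensory domains of perception"; no number is given for each direction of asymmetry.

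The protocol's Randomization paragraph fixes the coding: "We define visual-acoustic biofeedback as the congruent condition and ultrasound biofeedback as the incongruent condition for individuals with a primary auditory deficit". For children with the opposite profile, that paragraph swaps the two labels.

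The SAP section states that "a randomization test will be conducted for each participant", comparing ultrasound with visual-acoustic biofeedback on F3-F2, and that the comparison is replicated in 8 participants. It says that the asymmetry requirement "will allow us to use within-subject comparisons to test the hypothesis that sensory acuity in a domain mediates response" to the feedback aimed at that domain. It expects that not every child will reach significance, but that "those who do will show an advantage for the congruent over the incongruent condition, and not the reverse".

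**The concern.** Profile does not vary within a child. For a child with an auditory deficit, congruent minus incongruent is visual-acoustic minus ultrasound; for a child with a somatosensory deficit it is the same difference with the sign changed. A significant congruent result in one child is therefore what matching predicts and also what a generally better type predicts. The two explanations part only when children of different profiles are compared, and the available text plans no such comparison.

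The SAP's expectation of congruent advantages without reversals can be falsified, and it bears on the interaction when both profiles are enrolled. It is not a decision rule: it has no count of children, no treatment of reversals and no error rate. At stake is whether the study can state a result on its own hypothesis without choosing the criterion after seeing eight results.

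**Working it through.** **Plan's own figure.** The SAP gives power .80 at d2 = 1.0 with 10 observations per condition. A paired t-test on 10 within-day differences, two-sided .05 (alpha is not stated, so assumed) and noncentrality 1.0 × √10 on 9 df gives 0.803. This treats d2 as being in units of the SD of the within-day difference. The figure reproduces, but it is power for a type difference in one child, not for the interaction.

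**Set-up.** Units are SDs of the within-day difference, with a paired t per child as stand-in for the randomization test. M is a general advantage of one type, with no matching. Let p = P(child significant for the better type) and q = P(significant the other way). Of the 8 children, k have the profile matched to the better type. The plan states no reading rule, so two are compared:

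- Rule A: at least one significant congruent child, none reverse. False support = (1−q)^k (1−p)^(8−k) − (1−p−q)^8.
- Rule B: at least one significant congruent child in each profile, none reverse. False support = [(1−q)^k − (1−p−q)^k] × [(1−p)^(8−k) − (1−p−q)^(8−k)].

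**Identical true effects in all children.**

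- M = 0: p = q = .025. Rule A: .975^8 − .95^8 = .8167 − .6634 = .153. Rule B at 4:4: (.975^4 − .95^4)² = .0892² = .008.
- M = 0.5: p = .2928, q = .00035. Rule A at 4:4: .2498 − .0623 = .187. At k = 6: .4990 − .0623 = .437. With the split the other way (k = 2) it is only .1250 − .0623 = .063.

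**True effects varying between children with SD 0.5** (assumed; p and q averaged over a normal distribution).

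- M = 0: p = q = .1287. Rule A: .8713^8 − .7426^8 = .3322 − .0925 = .240.
- M = 0.5: p = .3753, q = .0257. Rule A at 4:4: .1372 − .0166 = .121. Rule B at 4:4: (.9011 − .1287) × (.1523 − .1287) = .018.

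| Rule | Between-child SD | M | 4:4 | 6:2 |
|---|---|---|---|---|
| A | 0 | 0 | 15% | 15% |
| A | 0 | 0.5 | 19% | 44% |
| A | 0.5 | 0 | 24% | 24% |
| A | 0.5 | 0.5 | 12% | 32% |
| B | 0 | 0 | 0.8% | 0.6% |
| B | 0 | 0.5 | 0.04% | 0.04% |
| B | 0.5 | 0 | 7% | 6% |
| B | 0.5 | 0.5 | 2% | 3% |

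**Across-child contrast.** Take each child's mean within-day difference and compare the two profile groups with a pooled t on 6 df. A general type advantage adds the same amount to both group means and cancels. Simulated error in the hypothesised direction was 2.45% to 2.57% at 4:4, 6:2 and 7:1, for M = 0, 0.5 and 1.0 and between-child SD 0 to 1.0.

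For a matching effect of 1.0 (group means +1.0 and −1.0), the noncentrality is 2.0 / √[(SD_b² + 1/10)(1/n1 + 1/n2)]:

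- SD_b = 0.5: 2.0/0.418 = 4.78 at 4:4, power 98%; 2.0/0.483 = 4.14 at 6:2, power 93%.
- SD_b = 1.0: 2.0/0.742 = 2.70 at 4:4, power 62%; 2.0/0.856 = 2.34 at 6:2, power 50%.

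**The case against.** Replicated single-case tests are the declared design, and the hypothesis predicts two opposite simple effects that those tests address directly. An interaction can be significant while one type is better in both profiles, so a contrast alone does not prove the hypothesis either. Nor is power clearly gained: at a matching effect of 1.0, Rule B has 96% and 62% at 4:4 (between-child SD 0.5 and 1.0) and 88% and 56% at 6:2, close to the contrast. One sentence adopting such a rule would be a smaller change.

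Much of this stands. It is why the fix keeps the single-child tests and adds a direction requirement. It does not remove the point, because the plan states neither rule. Even Rule B's error moves with between-child variation, while the contrast holds 2.5% in the hypothesised direction.

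A reader might infer three stronger things that the documents do not support:

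- That the design cannot test matching. It can if both profiles are enrolled, and the protocol defines both.
- That the plan carries a false-support rate of 15% to 44%. Those figures belong to one lenient rule that is not in the plan, and the larger ones to identical effects across children.
- That all 8 children could share a profile, so that matching and a better type become indistinguishable. That is true of an 8:0 sample, but neither document plans one.

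Part of the SAP and the Aim 3 text it cites are not available. A profile mix or decision rule may be stated there.

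**Conclusion.** The point holds for the available text: a hypothesis about profiles is to be tested by analyses that each contrast types within one child, with no formal between-profile test and no rule for combining the eight results. Its size is not one number. Depending on the unstated reading rule and on between-child variation, false support at 4:4 or 6:2 runs from well under 1% to 44% with a general advantage of 0 or 0.5 SD. This rests on normal differences, a paired t as stand-in, two-sided .05 per child and assumed between-child SDs, none of which the documents give. The change is a cheap improvement; the design itself need not be altered.

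**What to change.** Keep the 8 single-child randomization tests. Add to the SAP:

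- One across-child test with its alpha, comparing each child's mean within-day difference (visual-acoustic minus ultrasound) between the auditory-deficit and somatosensory-deficit groups.
- Both group means with intervals, and a rule that the hypothesis counts as supported only if the contrast is significant and the two means lie in the opposite directions predicted.
- The intended number per profile, as even as eligibility allows, and a statement that matching cannot be tested if all 8 share one profile.

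If the unavailable text already holds a rule or a mix, a cross-reference settles that part.

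The cost is a paragraph and one analysis of data already collected. The test is small, and the direction requirement can only lower the power shown above. The SAP expects only 9 to 10 eligible children, which limits how far the split can be balanced. Profile is not randomised, so the contrast shows an association with profile rather than its effect.
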